1. Distribution of changes in T cells from baseline to response evaluation.
2. Association between abscopal responses and T cell changes from baseline. Changes from baseline in immune responses will be summarized over the time course of the study and post treatment using descriptive statistics and graphical displays. The patterns of changes in immune parameters will be examined using exploratory statistical approaches to assess the relationship of changes in individual parameters to clinical outcomes. Mixed effects regression models and general estimating equations will be used to compare the patterns of change in immune response over time in the two treatment groups.

Changes from pretreatment to follow up levels of immunologic parameters and other parameters described above in irradiated tumors (and non-irradiated tumors) will be compared between the two treatment groups using descriptive statistics and graphical displays.

All patients will be followed for progression-free survival and overall survival. Kaplan-Meier curves for progression-free survival and overall survival will be provided to summarize the results.

1.24.1.2 29.2 Interim Analyses

A futility analysis will be conducted after 50% of the total 18-week RECIST responses (estimated median time to response ~14 weeks) for final analysis have occurred (i.e., N/2 of N). No accrual suspension is required to conduct the futility analysis. If at this point the relative risk of no response in the immunotherapy arm over the immunotherapy plus radiation arm is 1.0 or less, the study will be stopped for futility.

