10.0 Study Therapy [Atezolizumab]

10.1 Atezolizumab

Atezolizumab is an Fc-engineered, humanized, monoclonal antibody that binds to PD-L1 and blocks interactions with the PD-1 and B7.1 receptors. Atezolizumab is a non-glycosylated IgG1 kappa immunoglobulin that has a calculated molecular mass of 145 kDa.

In Arm A:

Patients with Urothelial cancer will receive either Nivolumab on Days* 1, 15, 29, 43 and 57 or Atezolizumab or Pembrolizumab on Days* 1, 22, 43, 64

(* - infusions will have a ± 3 days window to accommodate inevitable scheduling changes and holidays)

In Arm B:

Radiation is given to one lesion, 30 Gy in 3 fractions of 10 Gy each, over one week interval (with a minimum of 36 hours between each fraction), conformally or by intensity modulated radiation treatment to maximally spare normal tissue.

On the day of radiation (Day 1) immunotherapy is administered and repeated on the scheduled days. Patients will receive radiation on Day 1 and immunotherapy will be given ± 24 hr from Day 1.

Patients on both treatment arms will undergo re-imaging on Day 63 (± 7 days) (after completing 5 (after completing 4 doses of Atezolizumab) and every 9 weeks (± 7 days) for one year and every 12 weeks (± 7 days) thereafter.

The first dose will be administered on Day 1 (± 24 hrs) and repeated on Days 15, 22, 43 and 64. Radiation will be delivered every other day (with a minimum of 36 hours between each fraction), starting on Day 1. A dose of 10 Gy x 3 days will be tested.

Dose Calculations

Injection: 1200 mg/20 mL (60 mg/mL) colorless to slightly yellow solution in a single-dose vial.

For Advanced Urothelial Cancer: Atezolizumab is given every 3 weeks.

The recommended dose of Atezolizumab is 1200mg administered (flat dose) as an intravenous infusion over 60 minutes every 3 weeks until disease progression or unacceptable toxicity. If the first infusion is tolerated, all subsequent infusions may be delivered over 30 minutes. Do not administer Atezolizumab as an intravenous push or bolus.

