10.3 Dose Modifications

No dose reductions of Atezolizumab are recommended.

Withhold/Permanently Discontinue Atezolizumab for any of the following:

Adverse Reaction	Severity*	Dose Modifications
Pneumonitis	Grade 2 pneumonitis	Withhold dose ^a
	Grade 3 or 4 pneumonitis	Permanently Discontinue
Hepatitis	Aspartate aminotransferase (AST)/or alanine aminotransferase (ALT) more than 3 and up to 5 times the upper limit of normal or total bilirubin more than 1.5 and up to 3 times the upper limit of normal	Withhold dose
	AST or ALT more than 5 times the upper limit of normal or total bilirubin more than 3 times the upper limit of normal	Permanently discontinue
Colitis or Diarrhea	Grade 2 or Grade 3	Withhold dose ^a
	Grade 4	Permanently discontinue
Symptomatic Hypophysitis, Adrenal Insufficiency, Hypothyroidism, Hyperthyroidism	Grade 2	Withhold dose ^a
	Grade 4 Hypophysitis	Permanently discontinue
Hyperglycemia	Grade 3 or Grade 4	Withhold dose ^a
Nephritis and Renal Dysfunction	Serum creatinine more than 1.5 and up to 6 times the upper limit of normal	Withhold dose ^a
	Serum creatinine more than 6 times the upper limit of normal	Permanently discontinue
Ocular inflammatory toxicity	Grade 2	Withhold dose ^a
	Grade 3 or 4	Permanently discontinue
Infection	Grade 3 and above	Withhold dose ^a
Pancreatitis	Grade 2 and above	Withhold dose ^a
Recurrent Pancreatitis	Grade 4 or any grade of recurrence	Permanently discontinue
Increase in amylase or lipase > 2.0 times ULN	Grade 3 and above	Withhold dose ^a
Infusion-related reactions	Grade 2 and above	Withhold dose ^a
	Grade 3 or 4	Permanently discontinue
Rash	Grade 3 rash	Withhold dose ^a
	Grade 4 rash	Permanently discontinue
Myasthenic syndrome/myasthenia gravis, Guillain-Barré or meningoencephalitis	All grades	Permanently discontinue

^a Resume treatment when adverse reaction returns to Grade 0 or 1.

* Toxicity was graded per National Cancer Institute Common Terminology Criteria for Adverse Events, Version 4.0 (NCI CTCAE v4).

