11.3 Treatment modifications for Radiation Adverse Events

Dosing delay: except for radiation-associated mucositis and skin toxicity, the patient should have resolution or return to baseline of all grade 3-4 toxicities prior to the start of the next immunotherapy treatment.

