17.3.2 Safety Assessments

All patients who receive at least one dose of Immunotherapy will be considered evaluable for safety parameters. Additionally, any occurrence of a SAE from time of consent up to and including follow-up visits will be reported. Refer to safety reporting section 6.2

Safety will be evaluated for all treated patients using the NCI CTCAE version 4.03 (<http://ctep.cancer.gov>). Safety assessments will be based on medical review of AE reports and the results of vital sign measurements, physical examinations and clinical laboratory tests.

1.12.1.1 17.4 Criteria for Evaluation

1.12.1.1.1 17.4.1 Safety Evaluation

This protocol will be monitored by the WCM Data Safety Monitoring Committee which oversees the safety of all WCM investigator initiated clinical trials. The trial will be monitored for all adverse events, laboratory abnormalities, and serious adverse events at least once every 12 months. In addition, serious adverse events are monitored for all studies on a monthly basis.

1.12.1.1.2 17.4.2 Efficacy Evaluation

For the purposes of this study, patients should be re-evaluated for response every 9 weeks, in year 1, every 12 weeks in years 2 and 3. Confirmatory scans may also be obtained 4 weeks following initial documentation of objective response or progressive disease.

Response and progression will be evaluated in this study using the international criteria proposed by the Response Evaluation Criteria in Solid Tumors (RECIST) guideline (version 1.1). Patients will be followed for scans every 9 weeks for the first year or until disease progression and every 12 weeks after the first year or until disease progression.

Measurable and non-measurable lesions:

- Measurable disease: Measurable lesions are defined as those that can be accurately measured in at least one dimension (longest diameter to be recorded) as ≥ 20 mm (≥ 2 cm) by chest x-ray or as ≥ 10 mm (≥ 1 cm) with CT scan, MRI, or calipers by clinical exam. All tumor measurements must be recorded in millimeters (or decimal fractions of centimeters).
- Malignant lymph nodes: pathologically enlarged and measurable lymph node must be ≥ 15 mm (≥ 1.5 cm) in short axis when assessed by CT scan (CT scan slice thickness recommended to be no greater than 5 mm [0.5 cm]). At baseline and in follow-up, only the short axis will be measured and followed.

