Following the subject's written consent to participate in the study, all SAEs should be collected and reported, including those thought to be associated with clinical trial procedures. SAE terminology and severity grading will be based on (*i.e. CTCAEv4*).

The following categories and definitions of causal relationship to study drug should be used for all clinical studies:

- Certain: There is a reasonable causal relationship between the study drug and the AE. The event responds to withdrawal of study drug (dechallenge), and recurs with rechallenge when clinically feasible.
- Probable: There is a reasonable causal relationship between the study drug and the AE. The event responds to dechallenge. Rechallenge is not required.
- Possible: There is reasonable causal relationship between the study drug and the AE. Dechallenge information is lacking or unclear.
- Not likely: There is a temporal relationship to study drug administration, but there is not a reasonable causal relationship between the study drug and the AE.
- Not related: There is not a temporal relationship to study drug administration (too early, or late, or study drug not taken), or there is a reasonable causal relationship between another drug, concurrent disease, or circumstance and the AE.
- Adverse events classified as "serious" require expeditious handling and reporting to WCM to comply with regulatory requirements.
- All SAEs whether related or unrelated to the ipilimumab, must be immediately reported to WCM (by the investigator or designee) within 24 hours of becoming aware of the event. If only limited information is initially available, follow-up reports are required. The original SAE form must be kept on file at the study site.
- Collection of complete information concerning SAEs is extremely important. Full descriptions of each event will be followed by WCM. Thus, follow-up information which becomes available as the SAE evolves, as well as supporting documentation (e.g., hospital discharge summaries and autopsy reports), should be collected subsequently, if not available at the time of the initial report, and immediately sent using the same procedure as the initial SAE report.
- An overdose is defined as the accidental or intentional ingestion of any dose of a product that is considered both excessive and medically important. For reporting purposes, WCM considers an overdose, regardless of adverse outcome, as an important medical event.

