Forty patients per year will be randomized to the trial over ~ 3 years of accrual, assuming an accrual rate of approximately 20 patients per year for each cohort (see study calendar).

1.24.1.1 29.1 Statistical analysis

Both arms will run in parallel but will be analyzed separately. When the target accrual is met for a cohort, it will be closed to accrual even though other cohorts may still be accruing. Analyses will be done separately for each arm. Analyses will be similar for the two arms.

The primary objective of this study is the comparison of best overall response rates between each arm after start of treatment. Fisher's Exact test will be used to estimate 95% confidence intervals for the difference and to perform a one-sided test with an alpha level of 20%. Response rates for each arm will also be estimated at this level. With 56 patients treated under each modality, if the true responses are 20% and 40% in the immunotherapy alone and immunotherapy and radiation arms, respectively, we have a 90% probability of detecting a difference between modalities. Secondary objectives include time to disease progression and mortality. Median times for these events will be estimated with 95% confidence intervals. Graphical summaries will include Kaplan-Meier curves and log-rank tests which will be used to detect differences between treatments. Median survival and progression times will be estimated if sufficient events are observed. Cox proportional hazards regression will be used to account for baseline characteristics. Stratified exploratory analyses by type of cancer (renal cancer cell carcinoma or urothelial carcinoma) will also be performed.

Toxicities will be summarized per arm and prepared using Chi-square or Fisher's Exact tests, where appropriate.

Patient and disease characteristics will be summarized and compared at randomization between the two treatment arms using descriptive statistics and graphical displays. Although randomization will remove systematic biases we will test for differences in arms using Chi-square or Fisher's exact methods for categorical variables and t-tests or Kruskal-Wallis tests (with appropriate transformations of data if necessary for continuous variables). Differences in RECIST outcomes within each patient comparing non-irradiated and irradiated lesions will be summarized. Similar techniques will be used for exploratory analyses of the following:

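### Safety evaluability rests on immunotherapy alone, so an Arm B patient who is irradiated but never infused is not evaluable under the only explicit definition

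*Combined protocol and SAP*

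**What the plan says.** Section 17.3.2 gives the only explicit rule for who counts: "All patients who receive at least one dose of Immunotherapy will be considered evaluable for safety parameters". It then states that "Safety will be evaluated for all treated patients using the NCI CTCAE version 4.03", and does not define who is treated. It also states that "any occurrence of a SAE from time of consent up to and including follow-up visits will be reported". Section 21.7 repeats the collection of SAEs from consent: "all SAEs should be collected and reported, including those thought to be associated with clinical trial procedures". Section 21.4 puts all adverse events on a patient log.

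Section 29.1 plans the comparison. "Toxicities will be summarized per arm", using chi-square or Fisher's exact tests, and no analysis population is named. Toxicity with and without radiotherapy is a secondary objective (Protocol Summary and section 1.2).

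For Arm B, sections 6.2, 9.1 and 10.1 fix the order of treatment only loosely: "Patients will receive radiation on Day 1 and immunotherapy will be given" within 24 hours either side of Day 1. Section 27.2 holds treatment for toxicity and lets the principal investigator decide whether the patient resumes or is withdrawn.

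**The concern.** Arm B has two study treatments, and section 12.1 names both radiation and the antibody as investigational agents. The evaluability rule recognises only the one that both arms share. A patient in Arm A who is never infused has received no study treatment, so leaving that patient out loses no exposure. A patient in Arm B who is never infused may already have had one or more 10 Gy fractions. The rule can therefore leave out exposed patients in Arm B only.

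At stake is the secondary toxicity comparison. If a severe event soon after a fraction is why the infusion is never given, then the event being measured decides whether the patient is counted.

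**Working it through.** **Can the case arise?**

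1. The infusion may follow the first fraction by up to 24 hours (6.2, 9.1, 10.1).
2. Toxicity in that interval leads to a hold and possibly to withdrawal (27.2).
3. A patient withdrawn at that point has been irradiated and has received no immunotherapy. Under the explicit rule in 17.3.2 this patient is not evaluable for safety. On an ordinary reading of the second sentence in 17.3.2 the patient was treated and is included. Section 29.1 does not settle the matter.

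**Size.** The documents give no toxicity rate and no count of patients irradiated without infusion, so there is no figure of the plan to reproduce for safety. The plan's 90% power concerns response. Exact enumeration of the one-sided Fisher test at alpha 0.20, with 56 per arm and 20% against 40%, gives 0.902. That figure does not depend on the safety set.

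From the plan: 56 patients in Arm B (112 randomised 1:1). Assumed: k = 1, 2 or 3 patients irradiated but never infused, and either 6 or 11 toxicity events among the infused patients. In the worst case all k excluded patients had the event:

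- rate with everyone exposed = (events among infused + k) / 56
- rate under the immunotherapy-only rule = events among infused / (56 − k)

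| Events among infused | k | Everyone exposed | Immunotherapy-only rule | Difference (points) |
|---|---|---|---|---|
| 6 | 1 | 7/56 = 12.5% | 6/55 = 10.9% | 1.6 |
| 6 | 2 | 8/56 = 14.3% | 6/54 = 11.1% | 3.2 |
| 6 | 3 | 9/56 = 16.1% | 6/53 = 11.3% | 4.8 |
| 11 | 1 | 12/56 = 21.4% | 11/55 = 20.0% | 1.4 |
| 11 | 2 | 13/56 = 23.2% | 11/54 = 20.4% | 2.8 |
| 11 | 3 | 14/56 = 25.0% | 11/53 = 20.8% | 4.2 |

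Dividing by k gives about 1.4 to 1.6 points per excluded patient.

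**Direction.** Let E be all events among the 56, and let j of the k excluded patients have had one. The understatement is E/56 − (E − j)/(56 − k), which has the sign of 56j − kE. It is positive only when j/k exceeds E/56, that is, when the excluded patients had a higher event rate than the arm as a whole. With E = 14 and j = 0, the rate rises from 14/56 = 25.0% to 14/55 = 25.5% (k = 1) or 14/53 = 26.4% (k = 3).

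**The case against.** The strongest reply is that the plan does not clearly exclude anyone. The rule says who is evaluable without the word only, the next statement covers all treated patients, and 29.1 speaks simply of arms. This stands in part: the exclusion is not certain. What remains is one explicit criterion, one undefined term that conflicts with it, and a comparison with no named set.

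The second reply is that the data are not lost. SAEs are reported from consent and adverse events are logged, so an event severe enough to prevent the first infusion would probably be reported as serious. This also stands. Collecting an event does not, however, place the patient in the denominator or the event in the numerator of the per-arm test.

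The third reply is that the case is rare. The first infusion is planned for the same day as the first fraction and may precede it. 17.3.2 sets no time limit, so a patient whose infusion is delayed but later given remains evaluable. Only a patient who never receives any dose is affected. This is correct and keeps the point small.

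A reader might infer more from two other places:

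- Section 10.3, with a matching row in 9.3, withholds drug for "Serum creatinine more than 1.5 and up to 6 times the upper limit of normal", while inclusion criterion 5 in section 8.1 admits creatinine up to 3 times the upper limit. Those rows are on-treatment rules for adverse reactions, with a footnote on resuming, and do not clearly govern a first dose in a patient with a stable raised value.
- Section 11.3 asks for "resolution or return to baseline of all grade 3-4 toxicities prior to the start of the next immunotherapy treatment". This delays the next treatment, exempts mucositis and skin toxicity, and does not show that first infusions will be withheld.

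Nor is it right that the infusion can be held and the radiation cannot: the opening sentence of 27.2 is not limited to drug.

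**Conclusion.** The point holds as a minor defect of definition. Under the only explicit rule, an Arm B patient irradiated but never infused is not evaluable for safety. That rule does not fit the secondary toxicity objective, and it conflicts with the reference to all treated patients in the same section.

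The worst-case effect is about 1.4 to 1.6 percentage points per such patient. It rests on assumed counts (1 to 3 patients, 6 or 11 events among the infused) and on every excluded patient having had the event.

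A reader might conclude that the bias always makes radiotherapy look safer. The documents do not support that. Only Arm B can lose exposed patients, but the direction of the error depends on why they were not infused. Harm is understated where toxicity is the reason; if the excluded patients had no event, the Arm B rate rises slightly. Neither the primary analysis nor the sample size is touched.

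**What to change.** Replace the evaluability sentence in 17.3.2 with: *All patients who receive at least one dose of immunotherapy or at least one fraction of study radiotherapy are evaluable for safety.* Use the same set where 17.3.2 refers to treated patients, and name it in 29.1 as the population for the toxicity comparison. State there whether patients are analysed by assigned arm or by treatment received.

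The cost is one revised sentence in 17.3.2 and a short addition to 29.1. No new data are needed, because SAEs are already collected from consent and all adverse events are logged.

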1.0 Study Objective

1.3 1.1 Primary Objectives

The primary objective of this study is to estimate, in patients with metastatic renal cell/urothelial carcinoma, the best overall response (BOR; time from: 96 weeks) rates of immunotherapy alone and of immunotherapy plus radiotherapy (to a single metastatic site) and to estimate the difference in BOR rates between these two treatment groups.

1.3.1.1 1.2 Secondary Objectives

The secondary objectives are to estimate the progression free survival and overall survival for patients treated with immunotherapy and immunotherapy plus radiotherapy and to assess the toxicities related to these two treatment groups.

1.3.1.2 1.3 Exploratory Objectives

The following exploratory analyses will be performed: 1.) The examination of an association between clinical responses and anti-tumor immune responses; 2.) The comparison of changes in T cell subsets within tumors and in the peripheral blood at baseline versus at response evaluation.

1.4 2.0 Background

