Adverse event (AE) monitoring and reporting is a routine part of every clinical trial. The investigator will be required to provide appropriate information concerning any findings that suggest significant hazards, contraindications, side effects, or precautions pertinent to the safe use of the drug or device under investigation. Safety will be monitored by evaluation of adverse events reported by patients or observed by investigators or research staff, as well as by other investigations such as clinical laboratory tests, x-rays, electrocardiographs, etc.

1.16.1.2 21.2 Adverse Event Definition

An adverse event (also referred to as an adverse experience) can be any unfavorable and unintended sign (e.g., an abnormal laboratory finding), symptom, or disease temporally associated with the use of a drug, and does not imply any judgment about causality. An adverse event can arise with any use of the drug (e.g., off-label use, use in combination with another drug) and with any route of administration, formulation, or dose, including an overdose.

1.16.1.3 21.3 Adverse Event Characteristics and Related Attributions

CTCAE Version 4.0 will be used for tracking the Adverse Events in this study.

CTCAE term (AE description) and grade: The descriptions and grading scales found in the revised NCI Common Terminology Criteria for Adverse Events (CTCAE) version 4.0 will be utilized for AE reporting. A copy of the CTCAE version 4.0 can be downloaded from the CTEP web site (<http://ctep.cancer.gov>).

Attribution of the AE:

- Definite – The AE *is clearly related* to the study treatment.
- Probable – The AE *is likely related* to the study treatment.
- Possible – The AE *may be related* to the study treatment.
- Unlikely – The AE *is doubtfully related* to the study treatment.
- Unrelated – The AE *is clearly NOT related* to the study treatment.

1.16.1.4 21.4 Recording of Adverse Events

All adverse events will be recorded on a patient specific AE log. The AE log will be maintained by the research staff and kept in the patient's research chart.

1.16.1.5 21.5 Reporting of AE to WCM IRB

All AEs occurring on this study will be reported to the IRB according to the IRB policy, which can be accessed via the following link:

http://researchintegrity.weill.cornell.edu/forms_and_policies/forms/Immediate_Reporting_Policy.pdf.

1.16.1.6 21.6 Definition of SAE

A **serious AE or reaction** is any untoward medical occurrence that at any dose:

- results in death

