- AEs should be followed to resolution or stabilization, and reported as SAEs if they become serious. This also applies to subjects experiencing AEs that cause interruption or discontinuation of immunotherapy, or those experiencing AEs that are present at the end of their participation in the study; such subjects should receive post-treatment follow-up as appropriate.
- All SAEs must be collected which occur within 30 days of discontinuation of dosing or completion of the patient's participation in the study if the last scheduled visit occurs at a later time. In addition, the Investigator should notify WCM of any SAE that may occur after this time period which they believe to be certainly, probably, or possibly related to immunotherapy.

1.16.1.8 21.8 Pregnancy

Sexually active women of childbearing potential must use an effective method of birth control during the course of the study, in a manner such that risk of failure is minimized.

Before enrolling women of childbearing potential (WOCBP) in this clinical trial, Investigators must review the guideline about study participation for WOCBP which can be found in the GCP Manual for Investigators. The topics include the following:

- General Information
- Informed Consent Form
- Pregnancy Prevention Information Sheet
- Drug Interactions with Hormonal Contraceptives
- Contraceptives in Current Use
- Guidelines for the Follow-up of a Reported Pregnancy

Prior to study enrollment, WOCBP must be advised of the importance of avoiding pregnancy during trial participation and the potential risk factors for an unintentional pregnancy. The subject must sign an informed consent form documenting this discussion.

All WOCBP MUST have a **negative** pregnancy test within 72 hours **prior** to receiving immunotherapy. The minimum sensitivity of the pregnancy test must be 25 IU/L or equivalent units of HCG. If the pregnancy test is positive, the subject must not receive nivolumab or atezolizumab and must not be enrolled in the study.

In addition, all WOCBP should be instructed to contact the Investigator immediately if they suspect they might be pregnant (e.g., missed or late menstrual period) at any time during study participation.

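### SAE causality in Section 21.7 is judged against the study drug only, so radiotherapy-caused SAEs can be labelled unrelated and new ones after the collection window carry no notification duty

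*Combined protocol and SAP*

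**What the plan says.** Two causality scales are in force.

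- Section 21.3, under "Attribution of the AE", grades each AE as Definite, Probable, Possible, Unlikely or Unrelated to the study treatment.
- Section 21.7 covers SAEs and says that its "definitions of causal relationship to study drug should be used for all clinical studies". Its categories are Certain, Probable, Possible, Not likely and Not related, each defined against the study drug. *Not related* includes the case where "there is a reasonable causal relationship between another drug, concurrent disease, or circumstance and the AE".

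On collection, Section 21.7 says that "all SAEs should be collected and reported, including those thought to be associated with clinical trial procedures". The 24-hour reporting bullet begins "All SAEs whether related or unrelated to the ipilimumab"; ipilimumab is not a treatment in this trial, and Section 22.2.3 (Records and Reports) names it too. Collection of all SAEs runs to 30 days after dosing stops, or to completion of participation if the last scheduled visit is later. Beyond that, the investigator is to notify "any SAE that may occur after this time period which they believe to be certainly, probably, or possibly related to immunotherapy".

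The secondary safety objective in Section 1.2 is "to assess the toxicities related to these two treatment groups". The Protocol Summary words the same objective as toxicity by CTCAE 4.0 in each treatment group, without a relatedness condition.

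**The concern.** Radiotherapy to one lesion is the only planned difference between arms A and B. A causality scale that recognises only the drug has no natural place for harm caused by the randomised intervention. The late-notification sentence has the same omission.

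Two things are at stake. The first is attribution: the same event can carry opposite labels on two scales, and no rule says which prevails. A table of related SAEs drawn from the 21.7 labels would leave out radiotherapy harm, and that error can fall only on arm B. The second is capture: a radiotherapy-related SAE that first appears after the collection window may never reach the trial, whereas a late immunotherapy-related SAE must be notified.

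**Working it through.** No planned figure is involved, so there is none to reproduce. The check sets the passages side by side and then does one piece of date arithmetic.

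**Step 1. Classify one event on both scales.** Take an SAE that the investigator believes was caused by radiotherapy alone.

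| | Section 21.3 | Section 21.7 |
|---|---|---|
| Reference exposure | study treatment, which in arm B can include radiotherapy | study drug |
| Highest categories | Definite: clearly related to treatment | Certain and Probable: both need a causal link to the drug and response to drug withdrawal |
| Possible | may be related to treatment | needs a reasonable causal link to the drug |
| Result for this event | can be Definite | Not likely (follows the drug in time, no causal link) or Not related (another cause) |

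The withdrawal criterion also has no meaning for radiotherapy, which the Schema schedules on days 1, 3 and 5. An event to which the drug may have contributed can still be Possible under 21.7, so the problem is confined to events attributed to radiotherapy alone.

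**Step 2. Does the label affect collection inside the window?** No. Section 21.7 collects all SAEs, including procedure-associated ones, and requires 24-hour reporting whether related or not. Section 17.3.2 reports any SAE from consent through the follow-up visits. Section 29.1 summarises toxicities by arm and states no attribution filter. Total counts per arm therefore do not depend on the causality label.

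**Step 3. What is covered after the window?** Only SAEs thought "certainly, probably, or possibly related to immunotherapy". An event labelled Not likely or Not related in Step 1 falls outside. Section 21.7 does follow AEs already present until they resolve or stabilise, and reports them if they become serious. What remains uncovered is an SAE with new onset after the window.

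**Step 4. When does the window close?** Inputs: first scan at day 63 ± 7 (Section 6.2); off study at progression, then 30 days of follow-up (footnote k to the tables in Sections 15.0 and 16.0); last fraction on day 5 (Schema).

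- End of cover = off-study day + 30: 63 + 30 = day 93. With the scan window, 56 + 30 = day 86 to 70 + 30 = day 100.
- Time since last fraction = end of cover − 5: 93 − 5 = 88 days, with a range of 86 − 5 = 81 to 100 − 5 = 95 days.
- Counting from the last dose gives an earlier date: 57 + 30 = day 87 for nivolumab on day 57, or 43 + 30 = day 73 for a three-weekly drug last given on day 43. The off-study date therefore governs here.
- A patient who stays on immunotherapy is covered, whatever the cause, for up to three years plus 30 days.

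**The case against.** The strongest reply is that this is loose wording with little effect on the planned analysis. SAE collection inside the window does not depend on cause, and the toxicity summary in Section 29.1 is by arm without a relatedness filter. Section 12.1 lists radiation among the investigational agents, so an investigator could reasonably read the study drug in 21.7 as including it. Events already present at the end of participation continue to be followed. The day 63 example also depends on the patient coming off study at that scan: footnote k points that way, but Section 20.0 would keep some patients with tumour increase before week 12 on treatment, and those two passages need reconciling.

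Most of this stands, and it limits the point. A reader might infer that arm B toxicity as a whole is understated, that the planned safety comparison is biased in favour of arm B, or that late radiotherapy SAEs in general need not be reported. The documents do not support those readings. Total counts are protected, no related-SAE comparison is specified in Section 29.1, and the late gap opens only after the window and only for new-onset events. Nor is misclassification certain: 21.7 permits it on its literal wording, and 21.3 points the other way.

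The reply does not remove the conflict between the scales or the omission from the late-notification sentence. Section 12.1 does not amend the definitions in 21.7, and the late sentence names immunotherapy explicitly. The follow-up visits in Section 17.3.2 do not clearly close the gap either, because footnote k limits follow-up to 30 days after coming off study.

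**Conclusion.** The point holds in limited form. Sections 21.3 and 21.7 give two unreconciled scales, and the SAE scale leaves out the one randomised intervention. A treatment-related SAE table based on 21.7 would omit toxicity specific to arm B; all-cause AE and SAE totals by arm would be unaffected. After the window, a new-onset SAE attributed to radiotherapy alone has no stated notification duty. For a patient off study at the first scan, that begins at about day 93 (86 to 100), some 88 days (81 to 95) after the last fraction.

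This rests on three assumptions: that study drug is read literally, that the patient comes off study at the first scan, and that the off-study day counts as completion of participation. Later departure moves the closing date out day for day. The documents give no rate of radiotherapy SAEs, early or late, so neither the number mislabelled nor the number missed can be computed. The 56 patients planned for arm B are the number exposed, not an estimate of the number affected. The primary endpoint, sample size and efficacy tests are untouched. The correction should still be made, because it is cheap and concerns capture of harm from the treatment under test.

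**What to change.** 1. Use one attribution scale for AEs and SAEs in Sections 21.3 and 21.7, and record relationship to immunotherapy and relationship to radiotherapy as separate items.
2. Extend the late-notification sentence in Section 21.7 to SAEs related to immunotherapy or radiotherapy.
3. Replace the leftover ipilimumab in Sections 21.7 and 22.2.3 with the study treatments.

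The cost is protocol wording, one extra attribution field on the case report form, and slightly more late SAE reports. SAEs already reported could be re-attributed from the supporting documents that Section 21.7 requires. Treatment, visit schedule and sample size do not change.
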